7.0 Clinical and Laboratory Evaluations

Program Time Line

Study participants will be tested on multiple occasions. Information will be collected prior to surgery, followed by measurements on the day of procedure, and 2, 6, 12, 24, 52, and 104 weeks after surgery. Surgery will be performed on an arranged date with the orthopaedic surgeon. Physical therapy will follow a pre-defined protocol with a physical therapist.

Testing Visits

Outcome measures and safety measures will be collected at routine postoperative visits with the operating surgeon. Dates and involved events are described in Table 1 below.

Schedule of Events

Event	Pre-Procedure	Procedure Day	Post-Operative Week					
			2	6	12	24	52	104
Informed Consent	x							
Demographics	x							
Confirm Inclusion/Exclusion Criteria	x	x						
Medical History	x	x						
Vital Signs	x	x	x	x	x	x	x	x
Randomization		x						
Blood draw: Testosterone level and Oxandrolone level	x		x			x		
Blood draw: Liver Enzymes	x		x			x	x	x
Outcomes:								
MRI: rotator cuff healing; Sugaya classification (primary outcome)	x				x		x	x
MRI: Fatty infiltrate (secondary outcome)	x				x		x	x
MRI: Muscle volume (secondary outcome)	x				x		x	x
Body Composition – lean mass & body fat (secondary outcome)	x		x	x	x	x	x	x
Questionnaires: ASES, VAS, PASS (secondary outcome)	x	x	x	x	x	x	x	x
Shoulder Range of Motion (secondary outcome)	x	x	x	x	x	x	x	x
Shoulder Strength (secondary outcome)	x	x	x	x	x	x	x	x

Table 1. Outline of pre- and postoperative timing of events and schedule of data collection.

Demographics.

Demographics of age, height, weight, race, arm dominance, and tear size and location will be recorded.

Inclusion and Exclusion Criteria.

The inclusion and exclusion criteria will be confirmed prior to enrolled, as described above in section 5.0.

Females of reproductive potential (women who have not been post-menopausal for at least 24 consecutive months, ie, who have had menses within the preceding 24 months, or women who have not undergone surgical sterilization, hysterectomy or bilateral salpingectomy or bilateral oophorectomy or tubal ligation) must have a negative serum or urine pregnancy test *with a sensitivity of ≤ 25 mIU/mL* within 48 hours prior to study entry.

Females of reproductive potential must agree not to participate in the conception process (ie, active attempt to become pregnant, in vitro fertilization), and if participating in sexual activity that could lead to pregnancy, must use at least one reliable form of contraceptive. Female subjects must use contraceptives *while receiving study treatment and for 6 weeks* after stopping study treatment.

Protocol Number: APP-17-01020

Version Date: 9/1/2017

Acceptable forms of contraceptives include:

- *Condoms (male or female) with or without a spermicidal agent*
- *Diaphragm or cervical cap with spermicide*
- *Intrauterine device (IUD)*
- *Hormonal contraceptive*

NOTE: Written self-reported or partner reported sterility or lack of reproductive potential will be acceptable in place of contraceptive use.

Medical History.

A standard medical history questionnaire will be completed by the participant of past medical history of their shoulder pain, co-morbidities, and medical history of all other conditions.

Vital Signs.

Vital signs of temperature, blood pressure, respiration rate, and heart rate will be recorded.

Blood Draws

As described above, blood will be collected to monitor any adverse effects on the participant's health and to assess for medication compliance.

Outcomes:

MRI rotator cuff healing; Sugaya classification (Primary outcome). All participants will have a standardized MRI T2-weighted images without contrast, and used to classify rotator cuff integrity using 5 categories of the Sugaya classification. The 5 categories are: type I= rotator cuff sufficient thickness with homogeneously low intensity on each image; type II= rotator cuff sufficient thickness, partial high-intensity area; type III= insufficient rotator cuff thickness with less than half the thickness as compared to normal cuff, but without discontinuity; type IV= minor rotator cuff discontinuity with only 1 – 2 slices on imaging that suggest a small full-thickness tear; and type V= major discontinuity observed in more than 2 slices on imaging, suggesting a medium or large full-thickness tear.³³

MRI: Fatty infiltrate (Secondary outcome). All participants will have a standardized MRI T2-weighted images without contrast. The Goutallier grading classification⁷ will be used to assess fatty infiltration on 5 categories of grade 0= no fatty infiltration; grade 1= some fatty streaks; grade 2= less fat than muscle; grade 3= as much fat as muscle; and grade 4= more fat than muscle.

MRI – muscle volume (Secondary outcome). All participants will have a standardized MRI T2-weighted images without contrast, using the scapular plane of the sagittal-oblique image to measure supraspinatus muscle volume. Muscle volume will be measured by tracing the outer borders of the muscle, expressing the volume in mm^{2,34}.

Body Composition (Secondary outcome),

Study participants' lean mass and body fat percentage will be measured by bioelectrical impedance using Biospace InBody. The participant will have measurements at their preoperative visit and all postoperative visits.

Questionnaires (Secondary outcomes).

The participant will be asked to complete 3 questionnaires. Two questionnaires will be used to assess shoulder pain and function; American Shoulder and Elbow Surgeons Shoulder Assessment (ASES) to assess the patient-rated shoulder function on a scale of 0 -100 (0= no shoulder function/ disability), and a

Protocol Number: APP-17-01020

Version Date: 9/1/2017

Visual Analog Pain Scale (VAS) to assess the level of pain on a scale of 0 -10 (0 = no pain).¹¹⁻¹³ Patient satisfaction will be assessed with a single item question labeled the patient acceptable symptom state (PASS) questionnaire.^{11,14,15} The PASS is a 2-item question asking the patient their opinion of their current state of their shoulder, and if it is satisfactory for them. ASES, VAS, and PASS questionnaires at each visit to assess clinical outcomes.

Shoulder Range of Motion and Strength (Secondary outcomes).

Shoulder range of motion of flexion, abduction, external and internal rotation will be measured. During active range of motion, patients will be asked to move the shoulder as much as they can in the direction indicated by the investigator. Once participants reach their maximum range of motion, the measure will be recorded with a goniometer in degrees of motion. Two measures will be taken for each direction, and averaged for data analysis.

Shoulder strength will be measured using a hand-held device of: shoulder flexion, elevation on the scapular plane (scaption), external rotation, and internal rotation. The hand-held device (Hoggan Health Industries Inc., West Jordan, UT) is small device that contains a force transducer, measuring strength in kg of force. It is also commonly used in clinical settings, as it allows for accurate, and reliable measure. The arm of the patient will be positioned in a similar set of positions. The device will then be placed in contact with the distal segment. Participants will be asked to push against the device as hard as they can. Two measures for each movement will be collected. One-minute rest will be provided between measures.

Treatment

Orthopaedic Surgery

Rotator cuff repair will be performed by fellowship trained orthopaedic surgeons listed above.

Physical Therapy

Rehabilitation will follow a standard guideline under the supervision of a licensed physical therapist and the participant's physician.

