2.0 Objectives and Purpose

Specific Aim #1. Determine if oral Oxandrolone administration will improve rotator cuff healing following rotator cuff repair.

Oxandrolone is an orally administered synthetic derivative of testosterone that is approved by the Federal Drug Administration (FDA) in patients who have lost weight resulting from extensive surgery, severe trauma, chronic infection, or as an adjunctive therapy to promote weight gain. It is also approved for bone pain associated with osteoporosis, and to attenuate protein catabolism associated with the prolonged use of corticosteroids. Oral administration of Oxandrolone has demonstrated increases in lean mass, protein synthesis, and wound healing with no long-term adverse events in trauma patients as well as healthy male controls.¹⁻³ The aforementioned safety and efficacy profile of oral Oxandrolone makes it an appealing adjuvant treatment to counteract the major biologic consequences of a chronically torn rotator cuff (muscle atrophy, fatty infiltration, and intercellular fibrosis), which are known to lead to poor healing and diminished clinical outcomes.^{4,5} The primary aim of this double-blind, randomized study is to compare the rotator cuff healing rates between an experimental group receiving 12 weeks of daily, orally administered Oxandrolone following rotator cuff repair to a control group undergoing the same rotator cuff repair and receiving 12 weeks of a daily, orally administered placebo medication. The healing spectrum from complete healing to re-tear will be defined based on a previously validated diagnostic imaging metric. The primary outcome measure is rotator cuff muscle-tendon structural healing as measured by the Sugaya classification on magnetic resonance imaging (MRI) at the primary end-point of 6 months.⁶ We will continue to follow for one year. We hypothesize that those in the experimental group (Oxandrolone group) will have greater rotator cuff tendon structural healing as compared to the control (Placebo group) at the primary end-point of 6 months post-operative.

The secondary measure of healing will be the degree of fatty infiltration of the muscle-tendon unit on MRI using the Goutallier grading classification.⁷ We hypothesize that those in the experimental group (Oxandrolone group) will have less fatty infiltrate as compared to the control (Placebo group) at primary end-point of 1 year.

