8.0 Criteria for Evaluation and Endpoint Definitions

Outcome Measures

The primary outcome measure will be rotator cuff healing as measured by the MRI Sugaya classification.^{6,7} Measures will be performed at 12 weeks (the conclusion of Oxandrolone vs. placebo treatment), 6 months, 1 year and 2 years follow-up. The primary end-point will be 6 months.

Secondary outcome measures will include:

- 1) MRI evidence of rotator cuff fatty infiltration and muscle volume.
- 2) Patient-reported outcomes will be assessed with the ASES, a VAS, and PASS questionnaire.
- 3) Functional outcome will be assessed with shoulder range of motion with goniometer and isometric shoulder strength measures using a handheld dynamometer
- 4) Lean body mass and fat will be assessed with bioelectric impedance.

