10.0 Statistical Considerations

Statistical Methods

Descriptive statistics will be performed for participant demographics, historical information, intraoperative variables, as well as baseline testosterone, MRI measures of rotator cuff integrity, rotator cuff fatty infiltrate, rotator cuff muscle volume, shoulder strength, shoulder range of motion, patient-rated outcomes and body composition. Comparison for the primary outcome measure of rotator cuff integrity between groups from baseline to 1 year (primary endpoint) will be performed using a repeated measures analysis of Generalized Estimating Equation (GEE), appropriate for ordinal data. The GEE will also be used to compare between groups over time for the secondary outcome of fatty infiltrate (ordinal data). For all other secondary outcome variables, we will also use GEE for linear regression (ordinal data) or mixed model (continuous data) with repeatedly measured outcomes. Significance level will be established as $p < 0.05$. Analyses will be performed using STATA 13 software (College Station, TX) or SPSS and in consultation with the Statistics Department at USC.

Power Analysis and Sample Size

A power analysis for a sample size estimation was performed to detect a difference of 1 Sugaya grade (1-5 grades) classification (primary outcome) between the experimental and control group using 3 repeated measurements (baseline, 12 week, and 6 months).¹⁴ The power analysis was based with 2-sided alpha = 0.05 and power of 80%, and assuming a correlation among the repeated measures of 0.7 and overall SD of 2, giving a minimum sample size of 104 participants (n=52 participants in each group). This corresponds to an ANOVA effect size of 0.28 (28% of variance in primary outcome explained by treatment effect), or alternatively a moderate Cohen's D effect size (group mean difference divided by SD) of 0.5. Oversampling by 10% to account for possible attrition yields a total of 116 participants with 58 per group.

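### The time of the primary Sugaya MRI endpoint is contradictory: 6 months in sections 2 and 8, 1 year in the section 10 methods, and no week-24 MRI in Table 1

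*Combined protocol and SAP*

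**What the plan says.** **Section 2.0, Specific Aim #1.** The primary outcome is Sugaya grade on "magnetic resonance imaging (MRI) at the primary end-point of 6 months".

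**Section 8.0.** For the same outcome: "Measures will be performed at 12 weeks (the conclusion of Oxandrolone vs. placebo treatment), 6 months, 1 year and 2 years follow-up", followed by "The primary end-point will be 6 months".

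**Section 10.0, Statistical Methods.** The group comparison on the primary outcome "from baseline to 1 year (primary endpoint) will be performed using a repeated measures analysis". No contrast at a single time is named.

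**Section 10.0, Power Analysis and Sample Size.** The 104 participants (116 after attrition) rest on three readings, at baseline, 12 weeks and 6 months. This paragraph does not say which time is primary.

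**Section 7.0.** The text places visits at "measurements on the day of procedure, and 2, 6, 12, 24, 52, and 104 weeks after surgery", so week 24 is a visit. It then says "Dates and involved events are described in Table 1 below". In that table the row "MRI: rotator cuff healing; Sugaya classification (primary outcome)" is marked at pre-procedure and weeks 12, 52 and 104. The week-24 cell is empty, as it is in the other two MRI rows (fatty infiltration and muscle volume).

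**The concern.** Three parts of the plan that should agree do not: the definition of the endpoint, the schedule that produces the data, and the analysis that tests it. Two things follow.

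- **The measurement may not be taken.** Section 7 points to Table 1 for dates. A coordinator who books from it orders no MRI at week 24, and a 6-month scan that was missed cannot be recovered later.
- **The primary test is not fixed.** If section 8 is followed, 6 months and 1 year both carry the primary label at p < 0.05. If Table 1 is followed, the 6-month reading is absent, and weeks 12 and 52 are both available as substitutes. The selection risk therefore exists under either schedule.

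**Working it through.** **1. Count of scans.** The Sugaya row of Table 1, against the columns pre-procedure, procedure day and weeks 2, 6, 12, 24, 52 and 104, reads x, –, –, –, x, –, x, x: four marks. Section 8 lists four postoperative times, so with baseline it needs five. Shifting columns cannot create a fifth mark.

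The column positions are also supported by other rows. The testosterone row (before treatment, week 2, week 24) agrees with section 6, and the body-composition row agrees with its text in section 7. The liver-enzyme row does not agree with section 6; that is a separate matter to reconcile and does not alter this count.

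**2. Distance to the nearest scan under Table 1.** 24 − 12 = 12 weeks earlier; 52 − 24 = 28 weeks later.

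**3. The plan's sample size.** Inputs from section 10: difference 1 grade, SD 2, correlation 0.7, two-sided alpha 0.05, 52 per group. The mean of k equally correlated readings has SD = 2 × √[(1 + (k − 1) × 0.7)/k]. Power is from a two-sample t-test (noncentral t), for a 1-grade difference in that mean.

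| Readings used | k | SD of mean | Power at 52 per group | Needed per group |
|---|---|---|---|---|
| Baseline, 12 weeks, 6 months (stated basis) | 3 | 2 × √(2.4/3) = 1.789 | 80.6% | 52 |
| Baseline, 12 weeks (all that Table 1 supplies by 6 months) | 2 | 2 × √(1.7/2) = 1.844 | 78.2% | 55 |

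The first line reproduces the plan's 104 and its effect size: 0.5/1.789 = 0.28. With 10% attrition, 104/0.9 = 115.6, which rounds up to the plan's 116. Baseline, week 12 and week 52 also make three readings and give 104 under the same model, so the sample size alone cannot settle which time is meant.

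**4. False-positive rate if either time may be called primary.** For two separate tests at 0.05:
- identical results: 5%;
- independent results: 1 − 0.95² = 9.75%;
- correlation 0.7 (bivariate normal): about 8.3%.

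The plan gives 0.7 for its own repeated measures, not specifically for 6 months with 1 year, so using it here is an assumption.

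**5. Single-time power, for reference only.** On a 1–5 scale the variance at mean μ is at most (μ − 1)(5 − μ). With means 1 grade apart, the pooled within-group variance is largest at means 2.5 and 3.5: 1.5 × 2.5 = 3.75, so SD = 1.94. For a 1-grade difference at one time, 52 per group, unadjusted: about 74% at SD 1.94, 82% at 1.75 and 92% at 1.5. These are t-test approximations, not results for the ordinal GEE.

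**The case against.** **Six months is evidently meant.** Sections 2 and 8 agree, and the power paragraph stops at 6 months; against them stands one parenthesis in section 10. Nothing gives section 10 precedence, so a reader should not infer that its wording governs. This stands, and it makes the correction easy. It does not remove the error from Table 1 or from the methods paragraph, which are what a coordinator and an analyst would work from.

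**The scan may be taken anyway.** Section 8 lists it, and section 3 (Feasibility) has the coordinator confirm that postoperative MRI is completed. That duty carries no dates, so it does not close the gap. Equally, the documents do not show that the scan will be missed; that depends on which text the site follows.

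**Blinding limits selection.** Under section 5 the pharmacy releases group assignments at the end of the study, and investigators have no access to them during data collection. A correction made before release would be blind to group. This reduces the risk but does not remove it, because nothing requires the choice to be fixed by then.

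**The error-rate figure is an outer bound.** Section 10 plans one repeated-measures GEE, not two separate tests, and repeat scans of one tendon are unlikely to be independent. Both points stand: 9.75% is a ceiling under a stated scenario, not the plan's expected error rate.

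**A fourth conflict?** Section 2 says the oxandrolone group "will have less fatty infiltrate as compared to the control (Placebo group) at primary end-point of 1 year". A reader might count this too, but fatty infiltration is a secondary measure. It is loose wording and not part of the contradiction.

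**Conclusion.** The point holds as an internal inconsistency and should be corrected. The plan gives two primary times for one outcome and, in its schedule, no scan at the time that sections 2 and 8 name.

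- **If Table 1 is followed:** 0 of 116 participants have the 6-month reading. The main loss is the named primary outcome; the associated power loss is 2.4 percentage points (80.6% to 78.2%) under the plan's own model, which assumes correlation 0.7 throughout and a 1-grade difference in a mean that includes baseline.
- **Under either schedule:** more than one time could be presented as primary. For 6 months and 1 year tested separately, the false-positive rate is above 5% and at most 9.75%, about 8.3% at an assumed correlation of 0.7.

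A reader might go on to infer that the timing error leaves the trial underpowered. The documents do not support that: 104 reproduces from the stated inputs. That it was derived for an averaged effect and not for a single-time contrast is a separate matter, which needs only a clear statement.

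**What to change.** 1. **Table 1.** Mark the Sugaya MRI at week 24, as section 8 states. Say whether the fatty-infiltration and muscle-volume rows, which are also read from MRI and also empty at week 24, change with it.
2. **Section 10, methods.** Replace 1 year with 6 months as the primary endpoint. Name the treatment contrast at 6 months from the planned ordinal GEE as the single primary test, with the other times secondary.
3. **Alternative.** If 6 months is not intended, name one scheduled MRI visit as primary consistently in sections 2, 8 and 10, in Table 1 and in the sample-size basis. Either way, fix the choice before group assignments are released.
4. **Section 10, sample size.** State that 104 was derived for an effect averaged over three readings including baseline. If power for a single-time contrast is quoted, give it with its SD and label it a t-test approximation, as in step 5 of the working.
5. **Section 2 (minor).** Reword the 1-year time for fatty infiltration so that a secondary measure is not called a primary endpoint.

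**Cost.** A short amendment. Week 24 is already a visit and section 8 already plans the scan. If the site has been working from Table 1, the change adds one MRI per participant (up to 116). Participants already past week 24 without a scan would lack the primary outcome, so count them before the time is fixed.

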3.0 Study Design

Trial Design

This is a single-center, prospective 1:1 double blind randomized control trial. The trial will be conducted at the University of Southern California (USC), Keck School of Medicine in Los Angeles, California. Patients will be recruited from the Department of Orthopaedics. Men and women, 40–75 years of age, with MRI proven rotator cuff tears, indicated and scheduled for repair will be eligible for inclusion. Men and women with acute tears and those with significant comorbid liver, lung, cardiac, and kidney conditions will be excluded. Women who are pregnant or nursing will also be excluded. Women of child-bearing potential will be required to take a monthly urine pregnancy test and be on an agreed upon contraceptive. Participants will be randomized into one of two groups, a control group (receiving placebo medication) and an experimental group (receiving oral Oxandrolone, 12 mg twice daily for men and 6 mg twice daily for women for 12 weeks). Dosing will begin at the time of surgery and continue for 12 weeks, with medication dispensed by the USC Pharmacy. The study will be double-blinded: neither the treating surgeon nor the patient will know to which group the patient is enrolled.

Surgical Procedure

Arthroscopic inspection of the shoulder will be performed to verify the presence of a rotator cuff tear and to measure the size of the tear. In all cases a standard arthroscopic double-row technique will be used to repair the rotator cuff tendon.^{19,20} Treatment of the biceps tendon, need for subacromial decompression, and/or acromioclavicular joint resection will be at each surgeon's discretion. Intraoperative measurements of rotator cuff tear type and size as well as the details of the surgical procedure will be recorded.

Postoperative Rehabilitation

All participants in the study will undergo a standardized rehabilitation protocol for rotator cuff repair as agreed upon by the surgeons involved. Rehabilitation will be supervised by a licensed physical therapist. Adherence to the rehabilitation protocol will be assessed by review of patient treatment logs. If there are alterations to the standard postoperative rehabilitation course, the treating surgeon will be notified and will determine if the alteration in course warrants removal from the study. Patients who do not meet 80% adherence to the standardized protocol will be considered non-compliant and controlled for in the data analysis.

Feasibility

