- Fluid and Electrolytes: Retention of serum electrolytes (sodium chloride, potassium, phosphate, calcium).
- Musculoskeletal: Premature closure of epiphyses (in children).
- Dermatologic: Acne (especially in females and prepubertal males), hirsutism and male pattern baldness in females.
- Patients with moderate to severe COPD or COPD patients who are unresponsive to bronchodilators should be monitored closely for COPD exacerbation and fluid retention.

Contraindications: nephrosis, carcinoma of breast or prostate, hypercalcemia, pregnancy

US Boxed Warning:

Peliosis hepatitis: A condition in which liver, and sometimes, splenic tissue is replaced with blood-filled cysts which has occurred in patients receiving androgenic anabolic steroids. These cysts may be associated with hepatic dysfunction and even liver failure. This condition is usually completely reversible with cessation of drug.

Protocol Number: APP-17-01020

Version Date: 9/1/2017

Liver cell tumors: Most often benign and androgen-dependent, however, fatal malignant tumors have occurred. Withdrawal of the drug often results in regression or cessation of tumor progression. Hepatic tumors associated with androgens and anabolic steroids are much more vascular than other hepatic tumors and may be silent until life-threatening, intra-abdominal hemorrhage develops.

Blood Lipid Changes: Changes associated with increased risk of atherosclerosis are seen in patients treated with androgens or anabolic steroids, including decreased high-density lipoprotein (HDL) and increased low-density lipoprotein (LDL).

Pregnancy: Oxandrolone is classified as Category X in pregnancy due to teratogenic effects including embryotoxicity, fetotoxicity, infertility, and possible masculinization of the fetus.

Breast Feeding: It is unknown whether Oxandrolone is excreted in human milk. Because of the potential of serious adverse reactions in nursing infants from Oxandrolone, women who are nursing and do not wish to stop may not take part in the study.

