6.0 Study Agent Administration and Safety

Oxandrolone Administration

Oxandrolone will be given to experimental men (12 mg BID) and women (6 mg BID) for 12 weeks starting the day of surgery. Previous clinical studies where oxandrolone was given for greater than 6 months have shown no androgenic effects, behavioral changes, sepsis, hirsutism, or acne in the patient population. Elevated liver transaminase levels have been noted but have been transient and asymptomatic.¹⁻³

Patient Safety and Compliance

Patients will have liver transaminase levels measured when preoperative labs are obtained. Additionally, liver enzymes will be assessed at 2, 6, 12, and 24 weeks after rotator cuff repair. Testosterone levels and a quantitative assay for oxandrolone will also be drawn prior to supplementation, at the 2 week post-operative visit and at the 6 month post-operative visit to assess for compliance. Any adverse medication reaction will be met with cessation of medication, but will continue to be followed for outcome data collection.

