11.0 Registration Guidelines

At time of registration, two copies of a signed and dated participant's Informed Consent form with Bill of Rights must be available (an original for patient's medical chart; one copy for the patient, one copy for the research records)

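### The 48-hour pregnancy test is anchored to study entry, not to the first dose of a Category X drug; on one of two realistic readings the test can be older than 48 hours at dosing

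*Combined protocol and SAP*

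**What the plan says.** All references are to the combined protocol and SAP.

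- **Test window.** Section 7.0, under the inclusion and exclusion criteria, requires a negative serum or urine test of stated sensitivity (25 mIU/mL or better) "within 48 hours prior to study entry". This is the only pregnancy test with a time window. The same part says "The inclusion and exclusion criteria will be confirmed prior to enrolled, as described above in section 5.0".
- **First dose.** Section 6.0 gives the drug "for 12 weeks starting the day of surgery". Section 3.0 agrees.
- **Date of surgery.** Section 7.0, Program Time Line: "Surgery will be performed on an arranged date with the orthopaedic surgeon". No maximum interval from consent or enrolment is given.
- **Reason for the test.** Section 4.0 states that "Oxandrolone is classified as Category X in pregnancy" and lists pregnancy as a contraindication.
- **Other safeguards.** Section 3.0: "Women of child-bearing potential will be required to take a monthly urine pregnancy test and be on an agreed upon contraceptive". Section 7.0 adds that a woman whose sexual activity could lead to pregnancy "must use at least one reliable form of contraceptive". Section 5.0 excludes pregnancy, and any expectation of conceiving, from the Screening visit until 6 weeks after the last dose.
- **Table 1.** Consent is marked at Pre-Procedure, eligibility confirmation at both Pre-Procedure and Procedure Day, and randomization at Procedure Day only. There is no pregnancy-test row.

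**The concern.** The test exists to keep a pregnant woman from starting a teratogenic drug, so the event that matters is the first dose. The protocol uses another anchor and does not define it in the available text. If that anchor falls at a visit before surgery, a pregnancy that begins between the test and surgery, or was too early to detect at the test, need not be picked up before dosing, even though staff have followed the rule exactly.

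What is at stake is participant safety. The primary outcome, the power calculation and the analysis are not involved. Those affected are the women within the 40–75 age range who meet section 7.0's definition of reproductive potential, which includes women with menses in the preceding 24 months. Their expected number is not given.

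**Working it through.** The plan states no figure to reproduce. The check sets the timing rules side by side and adds one line of arithmetic.

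**Formula.** Let D be the time from study entry to first dose. The oldest negative test that satisfies section 7.0 at first dose is then 48 hours + D.

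**Which meanings of entry are realistic?**

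1. *Randomization.* Table 1 puts it on Procedure Day, and dosing starts that day. D is about 0, so the oldest compliant test is about 48 hours old. There is no gap.
2. *Enrolment at the pre-procedure eligibility visit.* The test requirement follows directly after the sentence on confirming criteria before enrolment, under the same heading, and the first eligibility check in Table 1 is at Pre-Procedure. D is then the wait for surgery, and the oldest compliant test is 48 hours + D. The documents give no value or upper limit for D.
3. *Consent or the Screening visit.* These are awkward readings. A window ending at consent would place the test before consent was signed, and one ending at screening would place it before screening.
4. *Registration.* Section 11.0 begins "At time of registration, two copies of a signed and dated" and goes on to the consent form, but puts no date on registration. It does not help to place entry.

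Two realistic readings remain, one with a gap and one without.

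**Illustration only.** If D were 1 to 6 weeks (an assumption, not in the documents), reading 2 would allow a test 2 + 7 = 9 days to 2 + 42 = 44 days old at first dose. If the monthly tests also began at entry, they would limit this to about a month, but their start is not stated.

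**Does another safeguard close the gap under reading 2?**

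| Safeguard | Covers the wait for surgery? | Expressly requires a test before dosing? |
|---|---|---|
| Procedure Day eligibility recheck (Table 1) | Yes | No; no repeat test is named |
| Monthly urine test (3.0) | Unclear; no start stated | No; not linked to the first dose |
| Contraception (3.0, 7.0) | Partly; the only stated window in 7.0 is during treatment and 6 weeks after | No |
| Exclusion from Screening onward (5.0) | Yes | No; an exclusion alone does not detect an unrecognized pregnancy |

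Each safeguard lowers the risk, but none guarantees a recent negative test at first dose.

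**After the fix.** With the window tied to the first dose, the oldest compliant test is 48 hours old whatever D is.

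**The case against.** The strongest reply is that Table 1 already supplies the answer. Randomization, an eligibility recheck and the first dose all fall on Procedure Day, and pregnancy is an exclusion criterion. A site that rechecks eligibility properly that day has to satisfy itself that the woman is not pregnant. For harm to follow, the site would have to adopt the earlier reading, conception would have to occur despite the contraception duty, and neither the monthly test nor the recheck could catch it. The trial has one center, so a single instruction to staff would settle the matter. The consent form was not available for review and may state the timing.

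Much of this stands. It makes the randomization reading well supported and keeps the severity down. It does not remove the point, because Table 1 does not say that the recheck includes a new test. Under the earlier reading, the earlier negative result already meets the only written rule.

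A reader might infer that the protocol lets women start the drug with no recent test, or that the start of the trial is ambiguous in many ways. The documents support neither inference. Testing is required, with a short window and a set assay sensitivity, and only two readings of entry are realistic.

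**Conclusion.** The point holds as a conditional gap. Under the randomization reading there is none. Under the pre-procedure enrolment reading, the compliant test can be older than 48 hours at first dose by exactly the wait for surgery, which is unstated and uncapped. No probability of exposure and no count of affected women can be derived from the documents, and the 9-to-44-day illustration rests wholly on an assumed wait.

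It would be wrong to infer that any woman will be dosed on an outdated test, since the text does not say which reading the site uses and several other safeguards apply. Severity is low to moderate. It is worth acting on because the drug is a teratogen, the written rule should by itself secure a recent negative test before dosing, and the remedy is cheap. There is no effect on sample size, alpha, power or analysis.

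**What to change.** In section 7.0, replace the study-entry anchor with: *a negative pregnancy test (sensitivity 25 mIU/mL or better) within 48 hours before the first dose of study drug, for example on Procedure Day before randomization*. Testing before randomization also means that a woman with a positive result is never allocated.

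Add a pregnancy-test row to Table 1 showing this test and the monthly tests, with a stated start for the latter. As an optional clarification, state that contraception begins at the Screening visit, to match the exclusion in section 5.0.

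The cost is one phrase, one table row and at most one extra urine test per woman of reproductive potential, at a visit already scheduled. If the sponsor already meant Procedure Day, the change only records existing intent.
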